4.2.1. Treatments Administered

Dosing of the medications does not need to occur at the same time. All subjects receive remdesivir as a 200 mg intravenous (IV) loading dose on Day 1, followed by a 100 mg once-daily IV maintenance dose for the duration of the hospitalization up to a 10-day total course. If subjects already received the loading dose prior to study enrollment, then start at 100 mg/day on Day 1. Any doses of remdesivir given prior to enrollment will be counted, so the total duration of remdesivir (i.e. pre-enrollment + on this trial) is 10 days (i.e., a maximum of 10 total infusions). Any doses of remdesivir were administered prior to study enrollment should be documented in Advantage eClinical as a concomitant medication given prior to Day 1. The duration of dosing may be adjusted by the site similar to what is described in the package insert and based on a subject's clinical course and ultimate disease severity.

For the baricitinib component, subjects receive either active product or placebo as follows:

- Baricitinib will be administered as a 4 mg orally (po) (two 2mg tablets) or dissolved for NG tube, daily for the duration of the hospitalization up to a 14-day total course.
- A placebo will be given as two tablets po or dissolved for NG tube, daily for the duration of the hospitalization up to a 14-day total course.
 - Any pre-study dexamethasone (max 1 dose per inclusion criteria) is not counted towards the 10-day course.

For dexamethasone component, subjects receive either active product or placebo as follows:

- Dexamethasone administered as a 6 mg slow IV push over 3 to 5 minutes daily for the duration of the hospitalization up to a 10-day total course.

- A placebo will be given as an equal volume normal saline, as a slow IV push daily for the duration of the hospitalization up to a 10-day total course.
- If site local standards use other means of administration (such as IV infusion), these may be used for both active and placebo after approval of the sponsor.
- Any pre-study dexamethasone (max 1 dose per inclusion criteria) is not counted towards the 10 day course.

Duration of therapy:

- IV remdesivir – up to 10 days while hospitalized (i.e., maximum of 10 total infusions pre-enrollment and during study).
- Oral baricitinib (or oral placebo) – 14 days while hospitalized (i.e., maximum of 14 total doses).
- IV dexamethasone (or IV placebo) – 10 days while hospitalized (i.e., maximum of 10 total doses).

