- All study medications stop on discharge from hospital.
 - Of note, if a subject is retained in the hospital for non-COVID-19 related issues and no longer requires supplemental oxygen and ongoing medical care (i.e., ordinal scale category 3), the PI may decide to discontinue all medications.
- If readmitted after discharge, see Appendix D Section 7.4 of the study protocol.

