6.4. Covariates and Subgroups

As additional secondary analysis, the primary efficacy outcome will be summarized within each of the baseline actual ordinal score subgroups (5 and 6). Analysis of all secondary outcomes will be performed in subgroups based on the baseline actual ordinal score.

Further subgroup analyses for the primary and key secondary efficacy outcomes will evaluate the treatment effect within the following subgroups:

- Prior Corticosteroid use
 - Yes / No
 - Dexamethasone on the day of randomization / not
 - Number of on-study dexamethasone/placebo infusion (9 vs 10). Some subjects who received dexamethasone on the day of randomization may skip their first post-randomization, on-study dexamethasone / placebo infusion and therefore receive only 9, rather than the expected 10, on-study infusions.
- Geographic region
 - US sites; Non-US sites
 - North American sites; Asian sites; European sites
- Duration of symptoms prior to randomization
 - Quartiles
 - <= 10 days; > 10 days
 - <= Median; > Median
- Race (White; Black/African American; Asian; Other)
- Comorbidities
 - None; Any
 - None, One, Two or more
 - Obese; Non-Obese
- Age (<40; 40-64; 65 and older)
- Sex (Female; Male)

- Randomized strata
 - 5 or 6 (separately) on ordinal scale used for randomization

Note: separate analyses for randomized/actual severity will only be performed if at least one subject is erroneously randomized into the incorrect baseline ordinal score stratum.

Additionally, analyses of all remaining secondary efficacy outcomes and the time to death by Day 15/29 outcomes will evaluate the treatment effect within the following subgroups (among subjects enrolled with baseline ordinal score of 5 or 6 only):

- Duration of symptoms prior to randomization (<= Median; > Median)
- Severity of disease
 - Randomization stratification: 5 or 6 (separately) on ordinal scale.
 - Actual ordinal score at baseline: 5 or 6 (separately) on ordinal scale.

Note: separate analyses for randomized/actual severity will only be performed if at least one subject is erroneously randomized into the incorrect baseline ordinal score stratum.

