8.2.1. Sensitivity and Corroborative Analyses of the Primary Endpoint

The primary analysis will be repeated in the As Treated analysis population and in the ITT analysis population. The tabular and graphical summaries described in the previous section will be replicated for this As Treated analysis ([Figure 5](#)) and by baseline ordinal score ([Figure 6](#) and [Figure 7](#)).

Sensitivity analyses will be performed using Cox proportional hazards models to estimate the hazard ratio or progression to mechanical-ventilation or death ([Table 16](#)). A Cox model will be fit with binary indicators for treatment group and actual baseline Clinical Status ordinal score (5 or 6) as well as a treatment * actual baseline Clinical Status score interaction terms. The models will be fit to the mITT analysis population. The treatment group hazard ratios and CIs will be reported for both sets of models and the interaction term p-value will be reported for the interaction models. The tabular summary will also include results from an analysis of time to death or mechanical ventilation controlling for age and duration of symptoms as continuous covariates and baseline d-dimer and CRP values as continuous covariates.

The primary analysis will also be repeated using the other subgroups defined in Section [6.4](#) in place of actual baseline Clinical Status. Each subgroup will be considered separately, and the tabular and graphical summaries described in the previous section will be replicated for each subgroup. A forest plot ([Figure 8](#), [Figure 9](#), [Figure 10](#), [Figure 11](#)) will be generated to display the overall treatment hazard ratio estimate and CI from each of the within-subgroup analyses ([Table 17](#)).

As noted in Section [6.4](#), analyses that take into account concomitant medication will be performed ([Table 18](#) and [Table 19](#)).

In addition, a forest plot will be generated for the “leave one out” sensitivity analyses described in Section [6.7](#) ([Figure 12](#)); estimated proportions and CIs will be provided for each subgroup that leaves a single site out.

Two corroborative summaries will also be generated. A summary of the number and percentage of subjects in each treatment group who:

- recovered (and are alive),
- did not recover and did not require mechanical ventilation or ECMO (and are alive),
- did not recover and required mechanical ventilation or ECMO (and are alive), and
- dead by Day 29.

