Table 18: Mechanical Ventilation Free Survival by Day 29 by Treatment Group: Prior Corticosteroid Use – mITT Population, Actual Baseline Ordinal Score 5 or 6

Table 19: Mechanical Ventilation Free Survival by Day 29 by Treatment Group: Medications of Interest Sensitivity Analysis – mITT Population, Actual Baseline Ordinal Score 5 or 6

Programming Notes for Table 17:

A “Subgroup” column will replace the “Model” column to the left of the “Treatment Group” column. Actual baseline ordinal score subgroups, prior corticosteroid use and medications of interest will not be included in this table. This table will include all other subgroups (see Section 6.4). P-values will not be included in this table.

Programming Notes for Table 18 and Table 19:

P-values will not be included in these tables.

A “Subgroup” column will replace the “Model” column to the left of the “Treatment Group” column. Actual Baseline Ordinal Score subgroups will not be included in this table.

A “Subgroup” column will replace the “Model” column to the left of the “Treatment Group” column. Actual Baseline Ordinal Score subgroups will not be included in this table. Separate models will be fit with censoring based on the first date of use for each of the following categories of medications (see Section 6.4).

- Any Medication of Interest
- Antivirals
- COVID-19 Vaccination
- Treatments for COVID-19
- Monoclonal antibodies targeting the spike protein of SARS-CoV-2 including casirivimab, imdevimab, and bamlanivimab.
- Renin-angiotensin system (RAS) Inhibitors and HMG-CoA reductase inhibitors (Statins)
- Corticosteroids
- Other Anti-Inflammatory Drugs

The table will include the following footnote: "In this analysis, subjects that reported use of the specified medications of interest are censored at time of medication receipt."

Table 20: Summary of Recoveries, Ventilator/ECMO Requirement, and Deaths by Day 29 – mITT Population

Grouping Variable	Actual Baseline Ordinal Score	Treatment Group	Recovered		Not Recovered and do not Require Mechanical Ventilation or ECMO		Require ECMO		Require Mechanical Ventilation		Require Mechanical Ventilation or ECMO		Deaths		
			n	%	n	%	n	%	n	%	n	%	n	%	
Actual Baseline Ordinal Score	5	Baricitinib + PBO + RDV (N=X)	x	x	x	x	x	x	x	x	x	x	x	x	
		PBO + Dexamethasone + RDV (N=X)	x	x	x	x	x	x	x	x	x	x	x	x	
	6	Baricitinib + PBO + RDV (N=X)	x	x	x	x	x	x	x	x	x	x	x	x	
		PBO + Dexamethasone + RDV (N=X)	x	x	x	x	x	x	x	x	x	x	x	x	

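### The nine-versus-ten-infusion subgroup is defined by a count that builds up after randomization, not by the skipped first infusion it is meant to capture

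*SAP*

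**What the plan says.** Section 6.4 opens its main list with "Further subgroup analyses for the primary and key secondary efficacy outcomes will evaluate the treatment effect within the following subgroups". Under prior corticosteroid use it gives a split on any prior use, then "Dexamethasone on the day of randomization / not", then "Number of on-study dexamethasone/placebo infusion (9 vs 10". The reason offered for the last item is narrow: "Some subjects who received dexamethasone on the day of randomization may skip their first post-randomization, on-study dexamethasone / placebo infusion", and would then end with nine infusions where ten were expected.

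Section 8.2.1 carries the list into the primary endpoint: "The primary analysis will also be repeated using the other subgroups defined in Section" 6.4, each subgroup taken separately. Table 18 is reserved for prior corticosteroid use, and Table 21 repeats the key secondary analysis for the Section 6.4 subgroups.

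Section 4.2.1 fixes how the count arises. Dexamethasone or its placebo is given "daily for the duration of the hospitalization up to a 10-day total course", and "All study medications stop on discharge from hospital". No landmark time or other handling is given for subjects with fewer than nine infusions.

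**The concern.** The purpose concerns something settled on Day 1: was the first on-study infusion left out because the subject had already had dexamethasone that day? The variable that is written down is a running total. To reach nine or ten, a subject must be alive, in hospital and still on study drug roughly 9 to 10 days after randomization.

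Three things follow.

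- Early deaths (primary events) and early discharges (mostly good outcomes) are removed from both levels.
- The nine-infusion level holds skippers who stayed the full course together with non-skippers who stopped after the ninth infusion. A skipper who goes home on Day 5 is in neither level.
- Membership depends on length of stay and survival, which treatment may change. If one arm discharges faster, the subjects left in that arm are a different selection from those left in the other.

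At stake is a published subgroup estimate that could look like an effect of prior dexamethasone, or of its timing, when it only reflects who remained in hospital. For the Day 15 ordinal score the selection is closer still, because being in hospital on Day 9 or 10 is part of the path to that outcome. No calculation was made for that endpoint.

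**Working it through.** **Yardstick.** The SAP states no figure for this subgroup, so the planned effect serves for scale. Table 1 takes 0.85 against 0.90, two-sided 5%, 80% power, total 1382. With n per arm = [1.960·√(2·0.875·0.125) + 0.8416·√(0.85·0.15 + 0.90·0.10)]² / 0.05², the result is 686 per arm, 1372 in total. That is within 1% of the exact-test figure of 1382. The planned effect is 5 points.

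**Who can enter either level.** Inputs are the median times to recovery from the earlier trial quoted in Section 2, used as a proxy for stay: 7 and 8 days overall, 5 and 6 on low-flow oxygen, 10 and 18 on high-flow or non-invasive ventilation (baricitinib and control respectively). Assuming exponential stay with median m, the share still in hospital for a ninth daily infusion is 0.5^(8/m), and for a tenth 0.5^(9/m).

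| Median (days) | Ninth infusion possible | Tenth infusion possible |
|---|---|---|
| 7 / 8 | 45% / 50% | 41% / 46% |
| 5 / 6 | 33% / 40% | 29% / 35% |
| 10 / 18 | 57% / 73% | 54% / 71% |

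So between 1 − 0.735 = 27% and 1 − 0.330 = 67% could not reach nine, and the share differs by arm whenever stay differs.

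**Null simulation.** Four million subjects per scenario, with the same risk of ventilation or death in both arms (true ventilation-free survival 0.860). All of the following are assumptions:

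- A shared latent severity raises event risk and lengthens stay.
- Events occur at an exponential time with mean 5 days. Of those subjects, 40% die after a further exponential time with mean 6 days; the rest stay in hospital.
- 15% skip the first infusion, independently of severity, and the omitted infusion is not made up (the Section 6.4 account).
- Dosing either continues or stops at ventilation, because the SAP does not say which.

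Ventilation-free survival, baricitinib against dexamethasone:

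| Dosing at ventilation | Stay medians | Ten infusions | Nine infusions |
|---|---|---|---|
| Continues | 7 vs 8 | 0.748 vs 0.767 (−2.0 points) | 0.800 vs 0.809 (−0.9) |
| Continues | 10 vs 18 | 0.794 vs 0.838 (−4.4) | 0.824 vs 0.844 (−2.0) |
| Continues | 7 vs 7 | 0.747 vs 0.747 (0.0) | 0.801 vs 0.800 (+0.1) |
| Stops | 7 vs 8 | 0.935 vs 0.942 (−0.7) | 0.909 vs 0.916 (−0.6) |
| Stops | 10 vs 18 | 0.950 vs 0.961 (−1.2) | 0.922 vs 0.933 (−1.1) |
| Stops | 7 vs 7 | 0.935 vs 0.936 (0.0) | 0.910 vs 0.910 (0.0) |

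The true difference is zero throughout. Across the scenarios, 22% to 38% of the nine-infusion level had not skipped the first infusion.

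**Same data, Day 1 definition.** Split by whether the first infusion was skipped, the arms agree at about 0.860 in both groups, within 0.2 points in every scenario, which is simulation error.

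**The case against.** The best defence is that the bullet is shorthand. It sits under prior corticosteroid use, its only explanation is the skipped infusion, and Section 3.3.1 describes the same people. On that reading, nine against ten labels the expected course, and the fault is loose wording. This is probably what was intended, but it does not rescue the text. The rule given is a number of infusions, Table 7 shows that counts from 1 to 10 are expected, and someone programming the rule as written would use the count.

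The consequence is also limited, and that part stands. Section 8.2 places these analyses outside the testing hierarchy as supportive. The notes for Tables 18 and 19 say "P-values will not be included in these tables", and Table 21 gives a treatment p-value only for its main analysis.

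The inputs are weak as well. The medians are times to recovery, not stay, and come from baricitinib against placebo, whereas this trial compares two active drugs. Section 2 itself warns that comparing the source trials is difficult. Equal stay in the two arms is possible, and the bias then vanishes.

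A reader might infer that the false effect could exceed the planned 5 points. A model with 13% events in each arm, every such subject staying at least 12 days, and one arm's stay 15% shorter does give 63% against 55% among those with ten infusions. But that keeps all events in the ten-infusion level, although death ends dosing. No scenario above that allows early deaths reaches 5 points. Nor can one infer that deterioration to ventilation drives the count: the SAP does not say that ventilation stops the infusions, so this driver is supported only through death.

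**Conclusion.** The point holds as a badly defined supportive subgroup. As written, the count is fixed after randomization, leaves subjects with fewer than nine infusions in neither level, and does not isolate the subjects it was meant to isolate. Under the stated assumptions the false difference in ventilation-free survival lies between about 0, with equal discharge speed, and 4.4 points. It depends on the proxy for stay, the link between severity and stay, and whether dosing continues on ventilation. In every scenario run with unequal stay, the faster-discharging arm looked worse, but other assumptions, such as a treatment effect on survival, could change the sign.

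Two stronger readings are not supported. One is that the contrast is non-randomised: the arms are still those assigned, and it is the subset that is selected afterwards. The other is that the trial's main result is compromised: no primary or key secondary conclusion rests on this bullet.

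**What to change.** In Section 6.4, replace the nine-versus-ten item with a Day 1 definition: first on-study dexamethasone/placebo infusion omitted because of a same-day pre-randomization dexamethasone dose, yes or no. That is settled on Day 1 under blinded treatment and covers all subjects. Carry the new label into Tables 18 and 21.

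Keep the listed split on dexamethasone on the day of randomization. It does not make the new item redundant, since only some of those subjects skip, so simply deleting the bullet would lose the question. Report infusion counts only as descriptive exposure in Table 7.

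The cost is one reworded bullet and one derived flag. Section 4.2.8 already records the date and time of each administration, and Table 11 already requires prior dexamethasone doses, so no new data should be needed.

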There will also be a sensitivity analysis of the primary, secondary, and mortality outcomes to evaluate the effect of concomitant therapy including experimental treatment and off-label use of marketed medications that are intended as treatment for COVID-19 and are given to patient prior to and during the study. A blinded review of the concomitant medication data will be performed by the medical monitor to identify medications that fall into any of the following categories of “Medications of Interest”:

- Vaccine for SARS-CoV-2 (Pfizer, Moderna, or other) including 1 or 2 doses received
- Antivirals
 - Protease inhibitors
 - Polymerase inhibitors
- Other Potential Treatments for COVID-19
 - Aplidin® (plitidepsin)
 - Colchicine (Colcrys)
 - Monoclonal antibodies targeting the spike protein of SARS-CoV-2 including casirivimab, imdevimab and bamlanivimab
 - Ivermectin (stromectol, Soolantra, Sklice)
- Corticosteroids
- Renin-angiotensin system (RAS) Inhibitors and HMG-CoA reductase inhibitors (statins)
- Other anti-inflammatory drugs
 - Monoclonal Antibodies Targeting Cytokines
 - Other Biologic Therapies

Summaries of subjects who report use of the categories and subcategories of therapies/treatments will be provided. Note that after the blinded review of the medications, additional categories/sub-categories may be defined and/or categories/sub-categories may be combined.

In addition, the sensitivity analyses will consider the following categories (individually):

- Any Medication of Interest
- Vaccines to SARS-CoV-2
- Antivirals
- COVID-19 treatments
- Monoclonal antibody treatments for COVID-19
- Corticosteroids
- RAS Inhibitors and HMG-CoA reductase inhibitors (statins)
- Other Anti-Inflammatory Drugs

Three initiation and duration groups will be constructed for each of the above categories:

1. Prior and During: Subjects taking medication of interest before randomization and during study (on or after Day 1).
2. Prior Only: Subjects taking medications of interest prior to randomization but stopping prior to randomization.
3. During Only: Subjects initiating medications of interest during the study (on or after Day 1).

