For the analysis of mechanical ventilation free survival, subjects will be censored at the time of medication/therapy initiation. For the analysis of the key secondary outcome, if a subject reports use of any of the medications/therapies prior to their Day 15 assessment, then the subject's last clinical status score prior to medication/therapy use will be used as their Day 15 outcome. For the mortality analyses, subjects will be censored at the time of medication/therapy initiation. For the analysis of the proportion of subjects that do not progress to Clinical Status Ordinal Score of 6, 7, or 8 by Day 29, subjects will be censored at the time of medication / therapy initiation. For the recovery analyses, subjects will be censored at the time of medication/therapy initiation. If a subject recovered prior to use of any of the medications/therapies, then the subject will still be counted as a recovery in the sensitivity analysis.

The effect of on-study treatment on select efficacy outcomes will also be explored among subjects who reported use of HMG-CoA reductase inhibitors (statins), angiotensin receptor blockers (ARBs), or angiotensin converting enzyme inhibitors (ACEIs) via subgroup analyses.

Lastly, the effect of treatment on the primary and key secondary efficacy outcomes will be explored via regression modeling controlling for age, duration of symptoms prior to randomization, baseline d-dimer, and baseline CRP values as continuous covariates.

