9.1.1. Prior and Concurrent Medical Conditions

Focused medical history is obtained at the screening visit that includes the following:

- History of chronic medical conditions related to inclusion and exclusion criteria
- Review medications and therapies for this current illness.

Medical history is limited to the following conditions: asthma, autoimmune hepatitis, cancer, cardiac arrhythmia, cardiac valvular disease, chronic kidney disease, chronic liver disease, chronic oxygen requirement, chronic respiratory disease, coagulopathy, congestive heart failure, coronary artery disease, current nicotine consumption, depression or psychotic disorder, diabetes I and II, epilepsy/seizure, hypertension, immune deficiency, obesity, systemic lupus erythematosus, and thyroid disease. History and risk factors for DVT/PE, major surgery in the past month, prolonged immobility, delivery in the past 6 weeks, pre-COVID oxygen use, blood type, and COVID-19 vaccination are also collected. All current illnesses and past pre-existing medical conditions will be MedDRA® coded using MedDRA dictionary version 23.0 or higher. Summaries of subjects’ pre-existing medical conditions will be presented by treatment group ([Table 56](#)).

Individual subject listings will be presented for all medical conditions ([Listing 8](#)).

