9.1.2. Prior and Concomitant Medications

Medication history (concomitant medications) includes a review of all current medications and medications taken within 7 days prior to enrollment through approximately Day 15 or early termination (if Day 15), whichever occurs first.

Summaries of medications that were started prior to dosing and continued at the time of dosing or started after dosing while on study will be presented by WHO Drug Level 1 and 2 Codes, actual baseline ordinal score, and treatment group ([Table 57](#)). Summaries of overall use of medications/therapies of interest listed in Section [6.4](#) that were started prior to dosing and continued at the time of dosing or started after dosing while on study as well as use by select study days will also be generated ([Table 58](#) and [Table 59](#)).

Individual subject listings will be presented for all concomitant medications ([Listing 9](#)), corticosteroid use ([Listing 10](#)), and medications of interest ([Listing 11](#)).

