	Native Hawaiian or Other Pacific Islander	x	x	x	x	x	x	x	x	x	x	x	x	x	x	x	x
	Black or African American	x	x	x	x	x	x	x	x	x	x	x	x	x	x	x	x
	White	x	x	x	x	x	x	x	x	x	x	x	x	x	x	x	x
	Multi-Racial	x	x	x	x	x	x	x	x	x	x	x	x	x	x	x	x
	Unknown	x	x	x	x	x	x	x	x	x	x	x	x	x	x	x	x
Geographic Region	Region 1	x	x	x	x	x	x	x	x	x	x	x	x	x	x	x	x
	...Continue for all region categorizations	x	x	x	x	x	x	x	x	x	x	x	x	x	x	x	x
Country	Country 1	x	x	x	x	x	x	x	x	x	x	x	x	x	x	x	x
	...Continue for all countries	x	x	x	x	x	x	x	x	x	x	x	x	x	x	x	x
Age	< 40	x	x	x	x	x	x	x	x	x	x	x	x	x	x	x	x
	40-64	x	x	x	x	x	x	x	x	x	x	x	x	x	x	x	x
	≥65	x	x	x	x	x	x	x	x	x	x	x	x	x	x	x	x

Demographic Category	Characteristic	Baricitinib + PBO + RDV						PBO + Dexamethasone + RDV						All Subjects					
		Baseline Ordinal Score 5 (N=X)		Baseline Ordinal Score 6 (N=X)		All Subjects ^a (N=X)		Baseline Ordinal Score 5 (N=X)		Baseline Ordinal Score 6 (N=X)		All Subjects ^a (N=X)		Baseline Ordinal Score 5 (N=X)		Baseline Ordinal Score 6 (N=X)		All Subjects ^a (N=X)	
		n	%	n	%	n	%	n	%	n	%	n	%	n	%	n	%	n	%
Blood Type	A+	x	x	x	x	x	x	x	x	x	x	x	x	x	x	x	x	x	x
	A-	x	x	x	x	x	x	x	x	x	x	x	x	x	x	x	x	x	x
	...Continue for all blood types	x	x	x	x	x	x	x	x	x	x	x	x	x	x	x	x	x	x
Duration of Symptoms prior to randomization	Categorization 1	x	x	x	x	x	x	x	x	x	x	x	x	x	x	x	x	x	x
	...Continue for all symptom categorizations	x	x	x	x	x	x	x	x	x	x	x	x	x	x	x	x	x	x
Comorbidities	Comorbidity 1	x	x	x	x	x	x	x	x	x	x	x	x	x	x	x	x	x	x
	Comorbidity 2	x	x	x	x	x	x	x	x	x	x	x	x	x	x	x	x	x	x
	...Continue for all comorbidities	x	x	x	x	x	x	x	x	x	x	x	x	x	x	x	x	x	x
Comorbidities Group X	...Continue for all comorbidity categorizations	x	x	x	x	x	x	x	x	x	x	x	x	x	x	x	x	x	x
COVID Vaccination	Yes	x	x	x	x	x	x	x	x	x	x	x	x	x	x	x	x	x	x
	No	x	x	x	x	x	x	x	x	x	x	x	x	x	x	x	x	x	x
Pre-COVID-19 Use of Supplemental Oxygen	Yes	x	x	x	x	x	x	x	x	x	x	x	x	x	x	x	x	x	x
	No	x	x	x	x	x	x	x	x	x	x	x	x	x	x	x	x	x	x

^a [X] additional subjects are included in the 'Any Clinical Status' row that were enrolled with a baseline ordinal score of 4. [Include as applicable]

Table 55: Continuous Demographic and Baseline Characteristics by Actual Baseline Ordinal Score and Treatment Group – mITT Population

Variable	Statistic	Baricitinib + PBO + RDV			PBO + Dexamethasone + RDV			All Subjects		

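### Vaccination in the Section 6.4 sensitivity analyses comes from medication data with a 7-day look-back, so many or most earlier-vaccinated subjects would count as non-users

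*SAP*

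**What the plan says.** SAP Section 6.4 plans sensitivity analyses for the effect of other COVID-19 therapies given before or during the study. The medications are to be identified as follows: "A blinded review of the concomitant medication data will be performed by the medical monitor". The first category listed is "Vaccine for SARS-CoV-2 (Pfizer, Moderna, or other) including 1 or 2 doses received". Each category is divided by timing into Prior and During, Prior Only, and During Only.

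Section 9.1.2 defines the data behind that review: "Medication history (concomitant medications) includes a review of all current medications and medications taken within 7 days prior to enrollment through approximately Day 15". Collection stops sooner for a subject who leaves the study before then.

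Section 9.1.1 has a separate item, collected with the medical history: "pre-COVID oxygen use, blood type, and COVID-19 vaccination are also collected". No look-back limit is stated for it. Table 54 reports it as a Yes/No row labelled "COVID Vaccination", by arm and baseline ordinal score. Nothing links this item to the Section 6.4 analyses, and vaccination is not among the baseline subgroups listed there.

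The rule for a user on the primary endpoint is: "For the analysis of mechanical ventilation free survival, subjects will be censored at the time of medication/therapy initiation". For Day 15 clinical status, the last score before use is taken as the outcome. COVID-19 Vaccination appears as a category or row for Tables 19, 21, 27, 32 and 73.

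**The concern.** A vaccine dose is a single event, not a continuing medication. A dose given 8 or more days before enrollment is neither current nor inside the 7-day window, so the stated source does not hold it. A subject vaccinated a month or more earlier would be analysed as a non-user.

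The plan also asks for detail that the window cannot reliably supply. Counting one or two doses needs a vaccination history, and a Prior Only group is mainly a record of past use.

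At stake is how five planned outputs are read. They cover the primary endpoint, Day 15 status, progression to score 6, 7 or 8, recovery, and mortality. A vaccination row that agrees with the main result could be taken as evidence that prior vaccination does not matter, when most vaccinated subjects may never have been identified. Tables 32 and 73 have a column for the number of users, but the Table 19 shell does not, so a reader of the primary-endpoint table could not see how few subjects the row had changed.

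**Working it through.** The plan states no figure for this point, so there is none to reproduce. The check sets the sections side by side and then bounds the size under stated assumptions.

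**Coverage of each source**

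| Vaccination event | Concomitant-medication data (9.1.2) | Medical-history item (9.1.1) |
|---|---|---|
| Dose more than 7 days before enrollment | Not covered | Covered; no look-back limit stated |
| Dose in the 7 days before enrollment | Covered | Covered |
| Dose on study to about Day 15 | Covered | Not covered, if taken at screening only |

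Section 6.4 uses only the first source.

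**Share of previously vaccinated subjects identified**

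Assume the last dose is uniform over the W days before enrollment. Share identified = 7/W.

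- W = 14: 7/14 = 50%, so 50% missed
- W = 30: 7/30 = 23%, so 77% missed
- W = 60: 7/60 = 12%, so 88% missed
- W = 90: 7/90 = 8%, so 92% missed
- W = 120: 7/120 = 6%, so 94% missed

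Now assume also that no dose is given in the last g days before enrollment because the subject is already ill. Share identified = (7 − g)/(W − g). With g = 5 this is 2/9 = 22% (W = 14), 2/25 = 8% (W = 30), 2/55 = 4% (W = 60) and 2/85 = 2% (W = 90). With g of 7 or more it is zero. On-study doses are left out of these shares; the stated source would catch them.

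**Subjects affected**

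Section 5 plans about 1500 subjects. The vaccinated share v is not in the SAP and is assumed at 1% to 20%. With W = 60:

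| v | Vaccinated, 1500 × v | Identified, 1500 × v × 7/60 |
|---|---|---|
| 1% | 15 | about 2 |
| 5% | 75 | about 9 |
| 10% | 150 | 17.5 |
| 20% | 300 | 35 |

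**Effect on the estimate**

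Take an overall risk difference of 0.05 (0.85 against 0.90, the planning scenario behind 1382 subjects in Table 1) and suppose no treatment effect in vaccinated subjects. If a fraction c of all subjects, all of them vaccinated, drops out of the analysis, the difference becomes 0.05/(1 − c).

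- v = 10%, 7-day source: c = 0.10 × 7/60 = 0.0117, giving 0.0506
- v = 10%, all identified: c = 0.10, giving 0.0556
- v = 1%, 7-day source: c = 0.01 × 7/60 = 0.0012, giving 0.0501
- v = 1%, all identified: c = 0.01, giving 0.0505

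The source matters at 10% vaccinated and hardly at all at 1%.

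**Would changing the source be enough?**

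No. A subject whose first dose precedes randomization, censored at first use, contributes no follow-up time. Under the Day 15 rule that subject has no on-study score before use. Neither rule suits an exposure completed before randomization.

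**The case against.** The strongest reply is that the real data may be better than the wording. Section 9.1.2 says that the history includes the 7-day review, which need not be its limit, and the case report form may record vaccine doses of any date as medications. The request for one or two doses suggests that the authors had a fuller record in mind, and Table 58, on-study use, has no vaccine row. Section 6.4 lets categories be added or combined after the blinded review, and Section 17 allows extra tables. These remain possibilities. None of them names the medical-history item as the source, and a programmer following the text would use the medication data.

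It can also be said that prior vaccination is a baseline attribute balanced in expectation by randomization, so that leaving it out of the subgroup list is no error. That is fair in itself. But the plan chose to examine vaccination, and its stated source is poorly suited to doing so.

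A reader might infer that almost every vaccinated subject is misclassified, and that the vaccination rows must reproduce the main result whatever the truth. The document does not support this. The share missed depends on dose timing that it does not give; on-study doses to about Day 15 would be caught; and with few vaccinated subjects even a correctly sourced analysis stays close to the main estimate.

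The objection on weight stands. These analyses lie outside the testing hierarchy (Sections 6.8 and 8.2), and the vaccination rows carry no p-values.

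**Conclusion.** The concern holds in limited form. As written, Section 6.4 draws vaccination from data that miss any dose completed more than 7 days before enrollment, while an item without that stated limit is collected and not used. Many or most previously vaccinated subjects would be classed as non-users: about 50% to 94% if the last dose is uniform over 14 to 120 days before enrollment, and up to all of them if no dose falls in the final week. Both the timing and the vaccination rate are assumptions.

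The vaccination rows of Tables 19, 21, 27, 32 and 73 are therefore a weak check. How far the estimate would move is unknown, and if few subjects were vaccinated it would move little under either source. The primary conclusion and type I error are unaffected. The correction is worth making because it is cheap and the rows would otherwise carry a label that their source cannot support.

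**What to change.** In Section 6.4:

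1. Derive baseline vaccination status (yes/no, and number of doses if recorded) from the medical-history item in Section 9.1.1.
2. Add it to the baseline subgroups, so that it is reported in Tables 17 and 21.
3. State that censoring at first use, and the last-score-before-use rule for Day 15 status, do not apply to vaccine doses given before randomization. Keep them only for doses first given after randomization, and label the vaccination rows of Tables 19, 21, 27, 32 and 73 accordingly.

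The cost is a change of SAP wording and one derived variable from data already collected. Table 54 shows only Yes/No, so the number of doses may not be available. The vaccinated subgroup may be small and its interval wide.
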